Note: Screening may continue during planned and unplanned SRC meetings. The protocol-specified Screening window may be extended to account for delays due to SRC meetings.

Recommendations by the SRC will include, but not be limited to: (a) evaluation of dose-modification and dose stopping criteria, (b) doses to be given in specified cohorts, (c) size of specified cohorts and (d) modification of the number and timing of PK and PD assessments (see [Section 4.4.1](#)).

Study Assessment and Procedures: Efficacy Assessments:

There are no therapeutic efficacy assessments in this study. Pharmacodynamic assessments will serve as surrogates for efficacy.

[figure not shown]
Pharmacokinetic Assessments:

For each cohort, blood samples to measure MYK-491 [REDACTED] plasma concentration will be drawn on each dosing day predose and postdose at serial timepoints as defined in the schedule of assessments. After review of the data, the SRC may decide that up to 2 additional blood samples should be obtained after each dosing period, or the timing of the samples should be modified to allow for acquisition of robust PK profiles.

[REDACTED]

Pharmacodynamics Assessments:

The PD effect of MYK-491 will be evaluated throughout this study by serial TTE examination in accordance with a standardized imaging protocol at Screening, before first DB dose (on Day 1, Day 2, and Day 3 morning predose), during DB treatment (Day 3 to Day 9), and during follow up (Day 10, Day 11) at defined timepoints (predose and/or 7h postdose) as defined in the schedule of assessments. The intent is to obtain a TTE at a timepoint close to the anticipated peak effect following each dose based on the PK profile. Throughout the study, in order to minimize variability of cardiac loading conditions for detecting changes in TTE assessments from DB treatment, every effort should be made to maintain stable background HF treatment and to administer such treatments (including diuretic as applicable) at the same time every day throughout the duration of the study. After review of the data, the SRC may decide to obtain up to 2 additional TTEs for each dosing period or the timing of the TTEs may be modified to obtain robust PD profiles. The primary echocardiographic variables of interest are LVSV (derived from LVOT-VTI), LVEF, LVFS, and SET. The sonographers will be trained and certified to perform the TTE by the Imaging Core Laboratory.

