6. Female patients must not be pregnant or lactating. Male patients (including men who have had vasectomies), as there may be a risk of drug being secreted in the ejaculate, should use barrier methods for the duration of the study and for 3 months after the last dose of study medication. All patients, if sexually active, must be using one of the following highly-effective birth control methods from the Screening visit through 3 months after the last dose of investigational medicinal product (IMP):

- Hormonal contraception associated with inhibition of ovulation, intrauterine device (IUD), or intrauterine hormone-release system (IUS) plus barrier (eg, male using condom or female using diaphragm or cervical cap)
- Vasectomy plus barrier
- Female is surgically sterile for 6 months or postmenopausal for 1 year. Permanent sterilization includes hysterectomy, bilateral oophorectomy, bilateral salpingectomy, and/or documented bilateral tubal occlusion at least 6 months prior to Screening. Females are considered postmenopausal if they have had amenorrhea for at least 1 year or more following cessation of all exogenous hormonal treatments, and follicle-stimulating hormone (FSH) levels are in the postmenopausal range.
- Male patients with postmenopausal partners

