8.2 Pregnancy

8.2.1 Avoidance of Pregnancy

Women of childbearing potential will be allowed to participate if they are not currently pregnant and/or breastfeeding and agree to not become pregnant for up to 3 months after the last dose of study medication. Women must use appropriate methods of birth control as listed in [Section 8.2.3](#). Women of nonchildbearing potential are defined as women who are permanently (surgically) sterilized or are postmenopausal. Permanent sterilization includes hysterectomy, bilateral oophorectomy, bilateral salpingectomy, and bilateral tubal occlusion or ligation at least 6 months prior. Women are considered postmenopausal if they have had amenorrhea for at least 1 year following cessation of all exogenous hormonal treatments and FSH levels are in the postmenopausal range. Pregnancy tests (urine or blood determined by local requirements [eg, only serum is acceptable in the UK]) should be performed on all females.

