investigator may add extra 12-lead ECG safety assessments if there are any abnormal findings or if the investigator considers it required for any other safety reason. If the patient has any signs or symptoms suggestive of possible cardiac ischemia, additional ECGs should be obtained. These assessments should be recorded as unscheduled assessments.

- ^h Changes in a Baseline condition after the ICF is signed but before IMP is administered are recorded on the medical history eCRF unless the change is considered an AE related to a study procedure. All changes that occur after administration of the study medication are recorded as AEs.
- ⁱ A full TTE must be performed at Screening. Two TTEs will be performed during screening, no fewer than 7 days apart. Eligibility must be confirmed by core laboratory for both TTEs. Effort should be made for the second TTE to be performed as close to time of dosing as is feasible, taking into account core laboratory processing time and patient availability. After the Screening assessment, abbreviated TTEs will be performed. It is important that the TTEs are completed as close as possible to the scheduled time. TTEs will be evaluated locally for changes that might affect dosing decisions for others in the cohort, but the official reading will be done centrally by experts in a core laboratory in a blinded manner with results provided to the SRC. The SRC may modify the timing of the TTEs after the initial cohort so that for each subsequent cohort a TTE is obtained at the time of the predicted peak pharmacological effect. This will be based on the PK and TTE profiles from the previous cohorts. If appropriate, the SRC can request up to 2 additional TTEs be obtained.

- ^k ECG telemetry will be initiated at least 1 hour predose and continued through at least 48 hours. Additional monitoring may be needed based on data and/or patient's tolerance to the treatment.
- ^l Blood sample for HIV, HCV, and HBV will be collected at Screening.
- ^m Pregnancy tests, urine or blood based on the policy of the local institution or regulating Health Authority (eg, requirement for serum-based testing in the UK), should be performed on all females at Screening, Day-1, and Follow-up.
- ⁿ FSH tests will be included for potentially postmenopausal women.

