APPENDIX 2 PART 2 SCHEDULE OF STUDY PROCEDURES - MULTIPLE, ASCENDING DOSES

Table 5 Part 2 (MAD): Screening, Dosing Periods, and Follow up – High-Level

		High-level Treatment and Observation												
Day	-28 to -1	1	2	3	4	5	6	7	8	9	10	11	12	16± 1
Period	Screen ^a	Baseline Single-blind Placebo BID		Double-blind Treatment BID								Follow Up		
CONFINED:														
Confinement in the unit ^b with telemetry		Admission	←						→	Discharge				
NON-CONFINED^b:														
Clinic visit mandatory ^c	X	AM, 3PM	AM, 7h	X (all day)	7h			AM		X (all day)	AM	AM	X	X
Clinic visit (optional) or HHN visit ^d		PM	PM		AM, PM	AM, PM	AM, PM	PM	AM, PM					
All Dosing and Assessments below apply to both CONFINED or NON-CONFINED Patients														
Informed consent	X													
Single-blind placebo administration		X Q12h	X Q12h											
Randomized DB IMP administration ^e				X Q12h	X Q12h	X Q12h	X Q12h	X Q12h	X Once (AM)					
Assessment of dose-modification/stopping criteria ^f		←							→					
Medical history	X													
Physical examination ^g	X	X		X				X±1d		X	X	X	X	
Body height	X													
Body weight	X			X							X			
Vital signs ^h	X	X	X	X	X	X	X	X	X	X	X	X	X	

High-level Treatment and Observation																								
Day	-28 to -1	1	2	3	4	5	6	7	8	9	10	11	12	16± 1										
Period	Screen ^a	Baseline Single-blind Placebo BID										Follow Up												
AEs/SAEs ⁱ	↔																							
Prior/concomitant therapy (incl. stable HF background treatment) ^j	↔																							
TTE ^k	X	X 3pm	X 0, 7h	X 0, 7h	X 7h			X 0h		X 0, 7hr	X 24h	X 48h												
ECG telemetry ^l		↔																						
Holter ECG ^m		↔						↔																
12-lead ECGs ⁿ	X		X 0h	X 0, 7h	X 7h			X±1d		X 0h	X 24h	X 48h		X										
ICD download ^o														X (± 1w)										
Serology ^p	X																							
Pregnancy test ^q	X													X										
FSH level ^r	X																							
Hematology ^s	X		X		X 7h			X±1d		X		X		X										
Chemistry ^t	X		X		X 7h			X±1d		X		X		X										
Urinalysis ^s	X									X														
Troponin ^t	X		X 0h	X 0,7h	X 7h			X±1d		X 0h	X 24h	X 48h		X										
NT-proBNP	X		X	X						X				X										

		High-level Treatment and Observation													
Day	-28 to -1	1	2	3	4	5	6	7	8	9	10	11	12	16± 1	
Period	Screen ^a	Double-blind Treatment BID												Follow Up	
PK (plasma) ^w				X Mult	X 0, 7h				X 0h		X Mult	X 24h	X 48h	X 72h	

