AE, adverse event; BP, blood pressure; bpm, beats per minute; CK-MB, creatine kinase-MB; DB, double-blind, [REDACTED]; ECG, electrocardiogram; eCRF, electronic case report form; HF, heart failure; HHN, home health nurse; HR, heart rate; ICD, implantable cardioverter defibrillator; ICF, informed consent form; IMP, investigational medicinal product; PK, pharmacokinetic; Pk/Tr, peak/trough; Q12h, every 12 hours; SAE, serious adverse event; SRC, Safety Review Committee; TTE, transthoracic echocardiography.

- ^a Patients with LVEF < 25% may be screened for up to 12 weeks to accommodate SRC review of first 3 patients of each cohort. Patients must remain clinically stable to meet eligibility.
- ^b **If a patient has an ICD, confinement is not required.** The patient may elect to stay in close proximity to the investigational site (eg, at a nearby hotel), but must return to the clinic for all IMP administrations and assessments. Alternatively, patients may be visited by a home health nurse for IMP administrations and assessments not requiring central equipment.. For all patients, ECGs, TTEs, and PK blood draws will be performed at the study site. If a patient is not confined, it is expected that the home health nurse will be in daily contact with the study site. All patients will be discharged from clinical research unit on Day 11 after all procedures have been completed and the investigator deems it safe.
- ^c For Day 3 and Day 9, a clinic visit from morning AM (pre-dose) until evening PM dose (12h later) is required. Refer to [Table 6](#) for a detailed schedule
- ^d Randomization will occur on Day 3 following local labs on Day 2. For patients who are not confined, some IMP administrations and assessments could be completed by a HHN. Days 1, 2, 4, 7 could have a HHN visit for the PM dose. Days 5, 6, 8 could utilize a HHN for both doses. Day 3 will require an in-clinic visit for both doses. Day 9 visit will be in-clinic and no evening dose and, therefore, no HHN visit. Days 10-12 assessments will be done on site.
- ^e For Cohorts D and E, and any additional cohorts, all IMP administration may be QD or BID for each dosing day, as determined by the SRC.
- ^f Further detail regarding dose-modification and stopping criteria are described in [Section 4.2](#).

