ⁿ Triplicate 12-lead ECG evaluations will be performed in the supine position after 10 minutes of rest at Screening and at Follow-up visit. See detailed schedule for Days 3 and 9. On Day 2, ECGs should be taken prior to the morning dose. On Day 4 ECG should be taken 7 hours post morning dose. On Day 7 (± 1 day) ECGs should be taken prior to morning dose. On Day 10, ECG is 24 hours post final dose and on Day 11 ECG is post 48 hours final dose. All predose ECGs should be taken within 2 hours of dose, and all other ECGs should be taken plus or minus 2 hours of time point indicated. The investigator may add extra 12-lead ECG safety assessments if there are any abnormal findings or if the investigator considers it required for any other safety reason. If the patient has any signs or symptoms suggestive of possible cardiac ischemia, additional ECGs should be obtained. These assessments should be recorded as unscheduled assessments. For all patients, ECGs will be performed at the study site.

^o ICD download to be performed unless site encounters significant technical difficulties and is required in case of shock(s) delivered by the ICD during the study.

^p Blood sample for HIV, HCV, and HBV will be collected at Screening.

^q Pregnancy tests, urine or blood based on the policy of the local institution or regulating Health Authority (eg, requirement for serum-based testing in the UK), should be performed on all females.

^r FSH tests will be included for potentially postmenopausal women.

- ^s Safety laboratory tests should be split and one sample evaluated by local lab and the other sent to Central Lab. Samples will be taken on days indicated prior to morning dose (except on Day 4, where labs will be taken at 7 hours post-dose). Day 2 local lab results must be evaluated prior to dosing on Day 3. If needed to accommodate local laboratory time tables, Day 2 samples may be taken on Day 1. Safety laboratory tests may be added at the discretion of the investigator. NOTE: Day 7 safety laboratory assessments can be performed ± 1 day if the assessments would fall on a weekend.

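### In Part 2 the only pregnancy test scheduled before first MYK-491 exposure is at Screening, up to about 30 days earlier (about 86 for LVEF < 25% patients held in Screening), whereas Part 1 retests on Day -1 of every dosing period

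*Combined protocol and SAP*

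**What the plan says.** Non-pregnancy is a condition of entry. Inclusion criterion 6 (Section 5.1) begins "Female patients must not be pregnant or lactating", and Section 8.2.1 adds: "Women of childbearing potential will be allowed to participate if they are not currently pregnant and/or breastfeeding". Section 8.2.1 also asks for pregnancy tests in all females but names no days, so timing rests on the schedules in Appendices 1 and 2.

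**Part 1.** Table 2 marks a test at Screening, on Day -1 of each of Periods A to D, and at Follow-up. Footnote m says that tests "should be performed on all females at Screening, Day-1, and Follow-up". Tables 3 and 4 repeat the Day -1 entry.

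**Part 2.** The pregnancy row of Table 5 has two marks, Screening and Day 16±1. Footnote q deals with method and ends "eg, requirement for serum-based testing in the UK), should be performed on all females"; it names no day. Table 6, the detailed schedule for Days 3 and 9, has no pregnancy row.

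**Length of Part 2 Screening.** Table 5 sets Screening at Day -28 to Day -1. Footnote a allows more: "Patients with LVEF < 25% may be screened for up to 12 weeks to accommodate SRC review of first 3 patients of each cohort". The Synopsis and Section 4.1.2 add: "The protocol-specified Screening window may be extended to account for delays due to SRC meetings". No maximum is given for that extension.

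**Checks before the first double-blind dose.** Section 6.1 requires eligibility to be reconfirmed before randomization. Table 5 footnote s says "Day 2 local lab results must be evaluated prior to dosing on Day 3".

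**The concern.** Pregnancy status can change between Screening and dosing, and a test at the start of a long Screening period says little about the day of exposure. Part 1 deals with this by retesting the day before each dose. Part 2 schedules nothing between Screening and the first active dose, although it is the part with repeated dosing and with the longer permitted Screening. The longest permitted gap falls on the LVEF < 25% patients waiting for a cohort to open.

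A site that followed Table 5 to the letter could therefore give study drug to a pregnant woman without breaching the schedule. Section 8.2.2 says that nothing is known about effects on the human fetus. What is at stake is participant safety and the enforcement of an eligibility criterion, not any estimate or analysis.

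**Working it through.** The plan states no figure for this gap, so there is none to reproduce. The check compares the two schedules, counts days, and looks for any other step that would supply a test.

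**1. Where the tests fall.** Counting across the columns of Table 5, the two pregnancy marks fall under Screening and Day 16±1. The 12-lead ECG row, which also ends with a mark at Day 16±1, confirms the alignment. The row is not blacked out. The last dose is on Day 9, so the Day 16±1 test follows all exposure. Before exposure, Screening is the only scheduled test.

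**2. Age of the last scheduled test at first possible active dose.** Days 1 and 2 of Part 2 are single-blind placebo, so first possible exposure is Day 3. There is no Day 0, so the gap from a negative day a to a positive day b is b − a − 1.

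- Part 1, Day -1 to Day 1: 1 − (−1) − 1 = 1 day.
- Part 2, tested on Day -1: 3 − (−1) − 1 = 3 days.
- Part 2, tested on Day -28: 3 − (−28) − 1 = 30 days.
- Part 2, LVEF < 25%, tested at the start of a 12-week Screening: 12 × 7 = 84 days to Day 1, plus 2 run-in days = 86 days.
- Part 2 with an SRC-related extension: no limit can be computed, because none is stated.

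Section 4.3 also allows scheduling time inside a second 28-day block. Taken as listed, that leaves 28 − 11 − 7 = 10 days. If all of it fell between Screening and Day 1, 30 days would become about 40. The protocol does not say where it falls, so I do not rely on this.

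**3. Does another step supply the test?**

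- Section 6.1 (reconfirm eligibility): no pregnancy test is named.
- Section 9.4.11 (local lab results reviewed and eligibility confirmed before dosing): this concerns safety laboratory tests. Appendix 4 lists pregnancy separately, among the nonsafety parameters.
- Table 5, Day 2: hematology, chemistry, troponin and NT-proBNP are marked; pregnancy is not.
- Footnote a (12-week Screening): asks only that patients remain clinically stable.

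**4. Exposure that follows.** In twice-daily Cohorts A to C an actively treated patient takes 6 × 2 + 1 = 13 double-blind doses (Days 3 to 8, then one on Day 9). A once-daily optional cohort would give 7.

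**5. Size of the risk under the required contraception.** Section 8.2.3 defines highly effective methods as failing in under 1% per year when used correctly. Assuming a constant rate, correct use and the 1% ceiling:

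- 30 days: 1% × 30/365 ≈ 0.08% per woman of childbearing potential.
- 86 days: 1% × 86/365 ≈ 0.24%.

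These figures cover conception during the gap only. They do not cover a conception shortly before Screening that the Screening test was too early to detect, or imperfect use.

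**The case against.** The strongest reply is that the interval is already protected. Criterion 6 and Section 8.2.3 require highly effective contraception or abstinence from Screening until 3 months after the last dose, and on the protocol's own ceiling the risk per woman is well under 1%. That stands as a statement about size. It does not make the test redundant: Part 1 carries the same requirement and still retests before every period.

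The difference could also be a deliberate choice. Exclusion criterion 13 accepts screening up to 12 weeks old for patients moving between parts if they are clinically stable. But no reason is given for dropping the predose test in Part 2. Those who cross from Part 1 to Part 2 also have later Part 1 tests (each Day -1 and Follow-up), so the gap mainly concerns direct entrants. The protocol does guard against outdated screening data elsewhere: a second screening echocardiogram is required, with effort to place it near randomization when windows are extended.

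Three stronger readings are tempting but unsupported:

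- That every Part 2 patient is dosed on a test 28 days to 12 weeks old. Those are upper limits. The test may be as late as Day -1, and 12 weeks applies to LVEF < 25% patients awaiting SRC review.
- That non-pregnancy goes unverified at dosing. Section 6.1 does require eligibility to be reconfirmed; what is missing is a scheduled test behind that step.
- That the gap equals a given number of ovulatory cycles at risk. The required contraception, part of which works by inhibiting ovulation, makes that count misleading.

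**Conclusion.** The point holds as a gap in the schedule. For patients entering Part 2 directly, no pregnancy test is scheduled between Screening and the first possible MYK-491 dose. The last scheduled test may be up to about 30 days old in the standard window, up to about 86 days old for LVEF < 25% patients held in Screening, and older under an SRC extension. Part 1's figure is 1 day.

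The 30- and 86-day figures assume a test on the first day of the window and the two-day placebo run-in. The documents give no count of women of childbearing potential; I assume that they are few. The probability of harm is low and the consequence for an affected patient could be serious. This is a low-cost improvement, not a defect in the trial's inference.

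**What to change.** Reconcile the Part 2 schedule with Part 1:

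- In Table 5, add a pregnancy test for women of childbearing potential to the Day 2 pre-randomization local labs, or to Day 1 where footnote s already lets those samples be drawn early.
- State that the result is reviewed with the other local labs before Day 3 randomization.
- Reword footnote q to name the test days, as Part 1 footnote m does.

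With this change the last scheduled test would be 1 or 2 days old at Day 3, however long Screening lasted. The cost is one table entry, one footnote, and a urine test or an added hCG on blood already being drawn, in a small subgroup. It needs no extra visit, staff or needle stick, and changes no endpoint or analysis.

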APPENDIX 4 LABORATORY ASSESSMENTS

The following safety laboratory parameters will be measured.

Table 9 Safety Laboratory Parameters

Hematology	Serum Chemistry	Urinalysis^a
• CBC, including differential count	• Sodium	• Specific gravity
• Platelet count	• Potassium	• pH
	• Chloride	• Protein
	• Bicarbonate	• Glucose
	• Calcium	• Leukocyte esterase
	• Magnesium	• Blood
	• Urea	
	• Creatinine	
	• ALP	
	• ALT	
	• AST	
	• Total bilirubin	
	• Glucose	
	• CPK	

ALT, alanine aminotransferase; ALP, alkaline phosphatase; AST, aspartate aminotransferase; CBC, complete blood count; CPK, creatine phosphokinase.

Urine microscopy will be performed if there is a significant abnormality in the dipstick.

Troponin I, Troponin T, [REDACTED] will also be assessed ([Appendix 1](#) and [Appendix 2](#)).

The following nonsafety laboratory parameters will be measured in this study:

- Serology (HIV, hepatitis panel)
- FSH
- Pregnancy, assessed in urine or blood based on the policy of the local institution or regulating Health Authority (eg, requirement for serum-based testing in the UK)

APPENDIX 5 POTENTIAL DRUG-INDUCED LIVER INJURY REPORTING AND ADDITIONAL ASSESSMENTS REPORTING

To facilitate appropriate monitoring for signals of drug-induced liver toxicity (DILI), cases of concurrent AST/ALT and TBL elevation according to the criteria specified in [Section 4.2](#) (3 times ULN for AST/ALT and 2 times ULN for TBL in patients with no underlying liver disease and eligibility criteria requiring normal liver function at Baseline) require the following:

- The event is to be reported to MyoKardia as an SAE within 24 hours of discovery or notification of the event (ie, before additional etiologic investigations have been concluded).
- The appropriate eCRFs (eg, Adverse Event eCRFs) that capture information necessary to facilitate the evaluation of treatment-emergent liver abnormalities are to be completed and sent to MyoKardia.

Other events of hepatotoxicity and potential DILI are to be reported as SAEs if they meet the criteria for an SAE defined in [Section 10.1.2](#).

Additional Clinical Assessments and Observation

All patients in whom investigational product(s) or protocol-required therapies is/are withheld (either permanently or conditionally) due to potential DILI or who experience AST/ALT elevations > 3 times ULN are to undergo a period of close observation until abnormalities return to normal or to the patient's Baseline levels. Assessments that are to be performed during this period include the following:

- Repeat liver chemistries within 24-48 hours (ALT, AST, alkaline phosphatase, TBL); in cases of TBL ≥ 2 times ULN or AST/ALT much greater than $3 \times$ ULN, retesting is to be performed within 24 hours.
 - Patients are to be monitored at least twice weekly; testing frequency may decrease to once per week or less if laboratory abnormalities stabilize or the investigational product(s) or protocol-required therapies have been discontinued AND the patient is asymptomatic.
- Obtain prothrombin time/international normalized ratio, fractionated bilirubin, and any other potentially relevant laboratory evaluations of liver function or disease.
- Obtain complete blood count with differential to assess for eosinophilia.
- Obtain appropriate blood sampling for PK analysis if this has not already been collected.
- Obtain a more detailed history of the following:
 - Prior and/or concurrent diseases or illness
 - Exposure to environmental and/or industrial chemical agents

- Symptoms (if applicable) including right upper quadrant pain, hypersensitivity-type reactions, fatigue, nausea, vomiting, and fever
- Prior and/or concurrent use of alcohol, recreational drugs, and special diets
- Concomitant medications (including nonprescription medicines and herbal and dietary supplements)
- Initiate full viral and autoimmune hepatitis evaluation (serologies for hepatitis A, B, C, D, E, Epstein-Barr virus, herpes simplex virus, etc.); evaluate for other potential causes of DILI, including but not limited to: nonalcoholic steatohepatitis, hypoxic/ischemic hepatopathy, and biliary tract disease.
- Obtain gastroenterology or hepatology consult.
- Perform appropriate liver imaging or biopsy if clinically indicated; strongly consider these tests in cases of concurrent transaminase and TBL elevation as specified in [Section 4.2](#).
- Follow the patient until all laboratory abnormalities return to Baseline or normal. The close observation period is to continue for a minimum of 4 weeks after investigational product(s) or protocol-required therapies discontinuation.

The potential DILI event and additional information such as medical history, concomitant medications, and laboratory results must be captured in corresponding eCRFs.

